Why is the participant leaving the study? (DATSTAT_EXITREASON)

Completed

Deceased

Censored (moved to a higher level of care- i.e. independent care to assisted living)

Unable to Continue (you should mark this answer if the person is too sick to continue)

Unable to Locate

Unwilling to Continue
Withdrawn by study staff
Unknown

What day did this person exit the study? (DATSTAT_EXITDATE)

What other information should we know about why this person left the study?
(DATSTAT_EXITCOMMENT)

Missing Data Points for a Participant

If study staff are not able to contact a participant within the appropriate window of data collection they have not exited the study but this is considered missing data. We will continue trying to contact the participant at every data collection point unless they contact us directly and ask to withdraw from the study. If research staff “miss” a data collection point, they should still try to collect the data but will have to follow the following protocol to ensure data is collected accurately:

Our DatStat workflow set up in your configuration is such that the time point gets updated when EITHER of the following occurs: 1) the survey for that timepoint gets submitted, OR 2) the time point goes out of window. For this participant, the 3 month call went out of window, and thus the timepoint got updated to 6 months.

In order to enter data for the 3 month survey at this point, the following must occur:

1. The participant must be edited and their time point set back to “3 months”
2. The current open survey (study task = “3 month survey”) must be closed by clicking Edit Survey next to the task in the Study Task grid, and changing the status to Final Incomplete
3. A new 3 month survey study task must be added. To do this, while in the study Task grid go to the Take Action menu and select Add Survey. Select the survey called “3 month Survey (Ad hoc)”. Schedule the survey, and select the Survey Pending status code, and click save. You may now use this task to enter your 3 month data. DO NOT do this until you’ve done steps 1 and 2.

Any time you make a change like this you need to mark down in your study log that you are making this change and mark down in your survey that this was collected out of window and the reason why. You also need to alert [name] that this change is made and she will record it in the data log,

Reentry into the study after exited**

If a participant has exited the study prematurely and contacts study staff about re-entry, the participant is only eligible to participate if

- a. They are still within the 1 year follow up period. In this case study staff will begin contacting participant at appropriate time points and other data will be considered missing.

- b. They sign a new consent form
- c. PI and Site PI agree to allow him/her to re-enter.

**Participants will never be allowed to collect more than \$100 for participation in the study

Payment

Completion of baseline= \$25

Completion of sixth month survey = \$25

Completion of endline survey at 12 months = \$50.

Regular Payment Schedule

Time Zero: \$25

12 Months: \$75

If a participant drops out after 6 months each organization will send the participant the \$25 they have earned.

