- A. One recruitment strategy will be to contact people off of a pre-specified list of people receiving peer to peer support or on the wait list to receive peer to peer support. These people are already receiving community services from Community Place. We will send out letters to the first 10 people on the list. The letter will give them the option to call us but it will also let them know that we will be calling them within the next two weeks to see if they are interested in participating in the research study. Research staff will select the next person to call and recruit to the study in the recruitment pattern according to the matching strategy that the biostatisticians prepared based on the sociodemographic breakdown of the clientele that are currently receiving peer to peer support. We will send out the *Introductory Letter* to potential participants on the wait list and to potential participants currently receiving peer to peer support. We will send out eligibility letters to people enrolled in peer-to-peer support and on the wait list simultaneously. Every 2-3 weeks we will send letters to 10 new people.
- B. A second recruitment strategy will be by making an announcement about the study at monthly training meetings for both Foster grandparent and senior companion programs. After the announcement is made, the research coordinator will approach potential participants at monthly training meetings and ask them if they are interested in learning more. If interested, we will tell them about the study, screen them for eligibility send them home with a consent form and set up a time to conduct the baseline interview. There is the possibility of enrolling 15-20 people at this meeting. This meeting occurs every month.
- C. A third recruitment strategy will be to hold informational sessions for the purpose of recruiting eligible participants for the study creating our "waitlist". These sessions will be held at community centers around town and in other venues where older adults frequent.

D. Community Place will be partnering with Star Program to recruit additional peers.

Recruitment Goal: As of February 23, 2016 the new recruitment goal at Community Place will be to recruit 226 participants into the study (113 experimental and 113 control)

Alpert Jewish Family and Children's Service

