The Alpert Jewish Family and Children's Service, West Palm Beach currently serves approximately 205 people who receive peer to peer support. There is not currently a waiting list so we will be recruiting people out of the community to serve as the control group. All people in both groups have access to all other services that the Jewish Family and Children's Service offers older adults in the community. People receiving peer to peer support will receive ID Numbers PB100E to PB499E and people receiving standard community services (on the wait list to receive peer to peer support) will receive ID numbers PB500C to PB999C.

A list of participants that are currently receiving peer to peer support will be uploaded into DatStat. However, only first name, age, date of birth, gender and race will be uploaded into the system. The Research Staff will keep a separate list of contact information for these participants on a secure file on her computer. Once a participant agrees to be in the study, then the additional contact information (phone number, address, last name) will be added into DatStat.

- A. One recruitment strategy will be to contact people off of a pre-specified list of people receiving peer to peer support. These people are already receiving services from the Jewish Family and Children's Service. We will send out letters to the first 10 people on the list. The letter will give them the option to call us but it will also let them know that we will be calling them within the next two weeks to see if they are interested in participating in the research study. Research staff will select the next person to call based on the number of people they are trying to recruit in each of the pre-specified categories (ex: white women 65-70). The biostatisticians have created a list of the number of people we should recruit in each demographic bucket based on the demographic breakdown of the people currently receiving peer to peer support. We will then send out the *Introductory Letter* to potential participants from the sessions (on the "wait list") and to potential participants currently receiving peer to peer support. We will send out eligibility letters to people enrolled in peer-to-peer support and to those who are eligible for peer to peer services simultaneously. Every 2-3 weeks we will send letters to 20 new people.

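### At Community Place, and for Los Angeles recipients, strategy A sets no contact order within a matching cell, so list position or staff choice could select who is enrolled

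*Protocol*

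**What the plan says.** Under Recruitment Strategies, strategy A for Community Place works from a list, fixed in advance, of current recipients and wait-listed people. The mailing rule is "We will send out letters to the first 10 people on the list", followed by ten more people every 2-3 weeks. For calls, "Research staff will select the next person to call and recruit to the study in the recruitment pattern according to the matching strategy" prepared by the biostatisticians. Strategy A for Jewish Family Service of LA uses the same wording.

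Four other provisions matter.

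- **Matching factors.** The Protocol (Matching) lists age group, gender and race/ethnicity, plus county at Community Place. The SAP (Randomization and matching) gives age, gender and race/ethnicity for both matched sites.
- **Visibility of group.** At Community Place the DatStat upload may include study group and companion name, and ID numbers end in E or C. The letter sent after a third failed recruitment call has a control and an experimental version.
- **Records.** Contact attempts are logged in DatStat. People found ineligible at pre-screen are deleted from it (Enrollment in Study). No record of why someone was chosen or passed over is described.
- **Analysis.** The SAP's primary analyses are two-sample tests without covariates. Regression on stratification factors, other potential confounders and site follows.

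Neither document states the order of the lists or a rule for choosing within a matching cell. The only random pick the Protocol describes is between two members of a couple.

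**The concern.** At the two matched sites the comparison rests on how well matching makes existing recipients and wait-listed people alike. Matching fixes the number in each cell. It does not fix which people in the cell are approached. If that depends on position in a list of unknown order, or on the judgement of staff who know the group, the enrolled people may differ from the rest of their cell in ways related to outcome, and differently in the two groups.

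The waiting list carries a specific risk. If it is kept in waiting order, its first names are the people nearest to receiving a companion. Controls drawn from there would be more likely to start peer support during follow-up, which would pull the two groups together.

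**Working it through.** **1. The plan's own figure.** SAP, Sample Size Justification: 720 participants, two-sided 0.05, effects of 0.209/0.223/0.242 SD. With 360 per group, power = Φ(d·√(360/2) − 1.96). For d = 0.209 this is Φ(2.804 − 1.96) = 0.801; the other two give 0.849 and 0.901. The stated 0.80/0.85/0.90 reproduce. A random contact order changes neither sample size nor power.

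**2. Room for order to matter.** Share needed = site goal / people listed (both from Recruitment Strategies).

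| List | Needed / listed | Share |
|---|---|---|
| Community Place, waiting list | 113/408 | 28% |
| Community Place, recipients | 113/210 | 54% |
| Los Angeles, recipients | 30/57 | 53% |
| Los Angeles, waiting list | 30/35 | 86% |

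The first three leave room for selection; the fourth leaves little.

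**3. Controls who start peer support, Community Place.** Assumptions, none of them in the documents: the list is in waiting order; 2, 5 or 10 companions free up per month; everyone approached consents and is eligible; all 113 controls come from the list; starts are spread evenly over 6 months; support has its full effect at once.

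- Served in 6 months = 6 × openings = 12, 30, 60.
- Share of the first 113: 12/113, 30/113, 60/113 = 11%, 27%, 53%. Share of a random 113: 12/408, 30/408, 60/408 = 3%, 7%, 15%.
- Exposed control person-time is half of each share: 5.3%, 13.3%, 26.5% against 1.5%, 3.7%, 7.4%.
- The 0.209 belongs to the whole trial, so the exposure is weighted by Community Place's part of the planned controls: 113/(113 + 150 + 30) = 113/293 = 38.6%.
- Pooled effect = 0.209 × (1 − 0.386 × exposure):

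| Openings per month | Head of list | Random order |
|---|---|---|
| 2 | 0.205 | 0.208 |
| 5 | 0.198 | 0.206 |
| 10 | 0.188 | 0.203 |

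With 360 controls instead of 293 (half of 720), the weight is 113/360 = 31.4% and the worst case is 0.209 × (1 − 0.314 × 0.265) = 0.192.

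**4. Selection on prognosis, Community Place (illustration only).** Let r be the correlation between list position and outcome, an assumption. Taking the first fraction f of a normally ordered list shifts its mean by r·φ(z_f)/f. The multiplier is 1.209 for f = 0.277 and 0.738 for f = 0.538. For r = 0.1, 0.2, 0.3 the false difference at this site is 0.05, 0.09, 0.14 SD if both lists lean the same way, and 0.19, 0.39, 0.58 SD if they lean opposite ways. For r = 0.1, multiplying by 226/586 = 38.6% gives 0.02 to 0.08 SD in the pooled comparison. These are upper bounds for each r: strict list order, full consent. For scale, a false difference of 0.05 or 0.10 SD across the 286 matched-site participants (226 + 60) would raise the two-sided error from 5% to 7% or 14%.

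**The case against.** The strongest reply is that this is only a gap in documentation. Staff select according to a strategy the biostatisticians prepared, which these documents do not reproduce, and the coordinating centre reviews the matching spreadsheet every month. Choice within a cell is therefore an inference at the matched sites. That is fair. But the review is described as monitoring how matching progresses, and no rule on order is stated.

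A reader might infer that list order and staff choice settle who represents every non-randomised group. They do not. Community Place also recruits at training meetings ("There is the possibility of enrolling 15-20 people at this meeting"), at information sessions and through a partner programme ("Community Place will be partnering with Star Program to recruit additional peers"). Los Angeles also recruits from Park LaBrea and/or meal programmes. Consent and screening select as well.

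A reader might extend the point to AJFCS, where "Research staff will select the next person to call based on the number of people they are trying to recruit in each of the pre-specified" demographic categories. The SAP calls that site randomised, so its call procedure is not evidence about the matched sites. The Protocol's account of recruiting existing recipients there does need reconciling with the SAP, but that is a separate matter.

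A reader might apply the Community Place exposure to the whole trial and report 0.209 falling to 0.153-0.198. That treats every control as a Community Place control; they are 113 of 293.

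A reader might also say that no planned analysis helps. The SAP plans adjusted regression and a comparison of AJFCS with the other two sites. These address measured differences and could signal inconsistency, but they cannot recover an unrecorded choice.

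Full consent is generous too. If half of those approached enrol (an assumption), 113 controls come from the first 226. The worst case is then 60/226 = 27% served and a pooled 0.198, against 0.203 at random. For recipients, the whole list is approached once enrolment falls to 54% at Community Place. The pool counts are also described as changing, and they precede the age and cognition filter.

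**Conclusion.** The point holds for strategy A at Community Place and for the Los Angeles recipient list. Letters follow an unstated order, staff who can see the group select whom to call, and no stated rule governs choice within a cell. The primary test does not address any selection that results, and the later regression does so only in part. The point does not cover the Los Angeles waiting list, AJFCS or people recruited by other routes.

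The size is unknown. Under the assumptions in step 3, the pooled 0.209 becomes 0.188-0.205, against 0.203-0.208 with random order: a modest loss even at the extreme. The prognostic figures in step 4 depend wholly on r. The documents do not show that either list is in waiting order, that companions go by queue position, or that staff favour healthier or more willing people, so none of these should be read as a finding. The case for change is that a clearly better procedure is available at little cost.

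**What to change.** For strategy A at the two matched sites, the biostatisticians put the recipient and waiting lists into random order within matching cell and group and load that order into DatStat. Letters and calls follow it. Each skip is logged with its reason, and each participant's recruitment route is recorded. Numbers approached, refused and enrolled are reported by group. People deleted at pre-screen should stay in a de-identified count so that these totals are complete.

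If recruitment has finished, state how the lists were ordered and report the same counts as far as the contact log allows.

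The cost is a short script, a Protocol sentence and some loss of scheduling convenience, with no extra participants. The change reduces selection within the lists. It does not reach the other recruitment routes, and it does not remove the underlying difference between existing recipients and wait-listed people. It lowers, but does not prevent, controls starting peer support.

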Appendix	
Introductory Letter for Participants (Community Place, AJFCS, JFS of LA)	
Failed Contact Recruitment Letter (Community Place)	
Reminder Letter (Community Place, AJFCS)	
Failed Contact 3, 6, 9, 12 month data collection (Community Place)	

Recruitment Strategies

Community Place

Community Place currently has 210 people receiving peer to peer support and 408 people on the wait list to receive peer to peer support. These numbers are fluid. All people in both groups have access to all other services that community place offers older adults in their community such as access to the Senior Center, various services we can connect with through our caseworker (Home delivered meals, benefits eligibility, Catholic Family Center-Elder one, Food link, Clothing services, legal consulting services, and Life span (Financial Budgeting, caregivers plan, HEP, High Cap-Health Insurance, Elder abuse prevention, and Rep pay program)).

All the people that are in the correct age range (≥ 65 years old) and have no known cognitive impairment will be uploaded into the study database in DatStat. People receiving peer to peer support will receive ID Numbers R100E to R499E and people receiving standard community services (on the wait list to receive peer to peer support) will receive ID numbers R500C to R999C. The following variables or a subset of these variables will be uploaded for all participants: ID, First Name, Last Name, Mailing Address, Phone, Age, Date of birth, gender, race, language preference, P2P program type, peer companion name, study group, RA first name, RA last name, RA telephone, RA email, Site PI.

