- A. One recruitment strategy will be to contact people off of a pre-specified list of people receiving peer to peer support or on the wait list to receive peer to peer support. These people are already receiving community services from JFS of LA. We will send out letters to the first 10 people on the list. The letter will give them the option to call us but it will also let them know that we will be calling them within the next two weeks to see if they are interested in participating in the research study. Research staff will select the next person to call and recruit to the study in the recruitment pattern according to the matching strategy that the biostatisticians prepared based on the sociodemographic breakdown of the clientele that are currently receiving peer to peer support. We will send out the *Introductory Letter* to potential participants on the wait list and to potential participants currently receiving peer to peer support. We will send out eligibility letters to people enrolled in peer-to-peer support and on the wait list simultaneously. Every 2-3 weeks we will send letters to 10 new people.
- B. A second recruitment strategy will be to recruit from Park LaBrea and/or meal programs that are put on by JFS of LA.

Recruitment Goal: As of February 23, 2016 the new recruitment goal at Jewish Family Services of Los Angeles will be to recruit 60 participants into the study (30 experimental and 30 control).

Contacting Potential Participants via the Telephone Prior to Enrollment in the Study (If we are unable to reach a potential participant via telephone, we will leave the following message.)

Hello {U:DATSTAT_FIRSTNAME}. My name is {U:RA_FIRST} {U:RA_LAST} from {U:DATSTAT_SITE}. I am calling to see if you would like to participate in a survey research study to better understand what helps older adults stay in their homes and communities. If you are interested in learning more about the Aging in Place study please call me back at {U:RA_TELEPHONE} and leave me a message if I'm not at my desk. Otherwise, I will call you back in one week to talk with you. If you are not interested in receiving any more calls from me about this study, please call me and let me know and I will not contact you again. Again, my name is {U:RA_FIRST} and my phone number is {U:RA_TELEPHONE} and I look forward to talking with you soon. Have a great day.

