For Community Place and Alpert Jewish Family and Children's Service (AJFCS), we are matching participants on the following characteristics: age group (<70, 70-80, and ≥ 80 years), gender (male and female), race/ethnicity (African American, Hispanic, and non-Hispanic White) and at Community Place we are also matching based on County (Monroe or Livingston).

At both all sites we are going to recruit people from the waiting list and match them with people already receiving peer to peer services. Every month research staff at UW will ask to see the matching spreadsheet as a way to monitor how matching is progressing at each site.

Enrolling more than one person per household (added 1/14/2016)

As of February 22, 2016, we will only enroll one person per household. This is the protocol for determining which person from the household we will enroll.

- a. If Participant A is enrolled in the study (signed the consent form) and they say they would like their partner would like to participate, the research staff person will let them know that according to study protocol we are only allowed to enroll one person per household. Participant A will be the person that is enrolled in the study.
- b. If prior to enrollment a study staff person is informed that both partners in a couple want to participate in the study. The staff person will let the two participants know that we can only enroll one participant from the couple. If we only need one person then the research staff will screen and enroll that person.
- c. If we know in advance there is a couple interested in participating and both people are needed for the study then we will randomly select one person per household. In this case you should screen both participants. If both participants are deemed eligible to participate you should first assign one participant heads and one participant tails. Then you should pull out the randomization envelope and open it. This envelope will tell you which participant you will enroll. At this time you will discard the envelope.

Enrollment in Study

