All medical records will be faxed to [name] in Madison, WI. Once we receive a patient's medical record we will enter the dates of hospitalizations and emergency department visits into DatStat using the Medical Record Review Form 1 and Medical Record Review Form 2. All medical records will be kept in a locked drawer in a locked office suite.

Accessing medical records for people who have died

If a participant dies prior to us accessing their medical records, we will request the legal guardian or spouse to sign a new form giving us permission to access their medical records.

Accessing medical records for people who withdraw from the study

If prior to the end of the study a participant withdraws from the study, we will ask them if it is still okay for us to access their medical records. We will remind them that they previously gave us permission to do so and that this will require no additional work on their part. If a participant agrees to this then we will follow the protocol above for accessing medical records.

Unexpected Circumstances

Some trouble shooting situations:

- If the client wants to give you food or drinks politely refuse and stress the quicker we can get the questionnaire done he/she can get back to their regular schedule.
- Participant gets tired in the middle of the questionnaire or you can tell they have lost their attention span to answer the questions. Try to complete study but if not you could try to finish questions over the phone making it easier so you don't have to go back to their homes. Payment will be sent to participant upon completion of the survey if applicable
- If there are interruptions (family comes home, friend comes by to visit, package gets dropped off, etc.) while questionnaire is being asked allow time for the participant to focus back to the task at hand.
- Canceling last minute may be an issue just be sure to make follow up phone calls to reschedule.
- Not home/forgot here the phone call the day before the scheduled time is important so they don't forget you are supposed to come over.
- For the control group a problem we may face is the fact that they don't know who the organization is and we could have higher refusals for that group.

Exiting the Study

At any time a participant has the right to exit the study. In this case you will answer the following questions on behalf of the participant and then they will not be contacted again for the purposes of the study.

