Randomization and matching In order to reduce potential bias further, participants from the AJFCS of Palm Beach will be allocated either to peer-to-peer support (Intervention) or standard community support (Control) in a 1:1 ratio using permuted block randomization, stratified by age, gender and race/ethnicity. Barring randomization in JFS of LA and Community Place of Greater Rochester, older adults already participating in peer-to-peer support and those on the waiting list will be matched on age, gender and race/ethnicity to mitigate potential differences between the two groups. In order to avoid reporting/ascertainment bias, calls will be made to all participating older adults and support staff at 3 and 9 months as outlined in Figure 4 above.

Sample Size Justification Given the total sample size of 720 at-risk older adults, the study has 0.80/0.85/0.90 power to detect the effect size of 0.209/0.223/0.242 for the primary outcome measure of the annualized rate of hospitalization, ED use and institutionalization at a two-tailed significance level 0.05. The effect size here is defined as the difference in the mean annualized rate of hospitalization, ED use and institutionalization between the two groups divided by the standard deviation of the annualized rate assumed to be common in the two groups. Due to random drop-out or loss to competing event of death, the study will have less power to detect the stated effect sizes or will have the stated power for larger effect sizes.

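### The SAP names the waiting list as the control source at the non-randomised sites, but Community Place also builds a study-made waitlist from community sessions, and no listed variable or planned analysis tells the two apart

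*Protocol*

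**What the plan says.** **SAP, Randomization and matching.** At Los Angeles and Community Place, "older adults already participating in peer-to-peer support and those on the waiting list will be matched on age, gender and race/ethnicity". No other control source is named.

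**Protocol, Matching.** The same source is given for the sites generally: "we are going to recruit people from the waiting list and match them with people already receiving peer to peer services". The matching factors are age group, gender and race/ethnicity, plus county at Community Place.

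**Protocol, Community Place.** Strategy A recruits from a list of recipients and wait-listed people, and says of them: "These people are already receiving community services from Community Place". Strategy C is different: "A third recruitment strategy will be to hold informational sessions for the purpose of recruiting eligible participants for the study creating our" waitlist, a word the protocol itself puts in quotation marks. "These sessions will be held at community centers around town and in other venues where older adults frequent". Every control gets an ID in the range R500C to R999C, under the single description of being on the wait list. The list of variables to upload has no item for recruitment source.

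**Protocol, Jewish Family Service of LA.** Strategy B reads: "A second recruitment strategy will be to recruit from Park LaBrea and/or meal programs that are put on by JFS of LA". It does not say which arm it feeds.

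**SAP, Analysis Plan.** The primary comparison is an unadjusted two-sample test. Later regressions adjust for stratification factors, site and other potential confounders that are not named.

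**The concern.** A control from the agency's own waiting list has asked for a companion and, under strategy A, already uses the agency. Such a person differs from a recipient mainly in not yet having a companion. Someone met at a community-center session may never have used the agency or asked for help. Against that control, the recipient differs by the companion, by agency contact and by help-seeking.

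Matching on demographics and county does not balance those last two differences, and an unadjusted test does not remove them. The SAP also plans to compare the effect at Palm Beach with the effect at these two sites to judge whether the designs agree. A difference in where controls came from could then be misread as a difference between randomised and matched designs.

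**Working it through.** **1. The plan's own figure.** Per-arm n = 2(z₀.₉₇₅ + z₀.₈₀)² / d² = 2(1.960 + 0.842)² / 0.209², which rounds up to 360, or 720 in total. This reproduces the SAP. The other two pairs (0.85 at 0.223, 0.90 at 0.242) give 724 and 718, which agree within rounding. The figure is used below only as a yardstick.

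**2. How much of the control group is exposed.** Control targets in the protocol are Community Place 113, Los Angeles 30 and Palm Beach 150.
- The two non-randomised sites supply 113 + 30 = 143 controls.
- All sites supply 143 + 150 = 293, so the share is 143/293 = 0.488.

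**3. Demand on the real waiting lists**, before eligibility screening, refusal and matching.
- For the larger of the two sites, the protocol gives these counts: "Community Place currently has 210 people receiving peer to peer support and 408 people on the wait list to receive peer to peer support". 113/408 = 28% of the list is needed.
- Los Angeles: 35 are listed for 30 places, so 30/35 = 86% is needed.

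**4. Bias under stated assumptions.** Let f be the share of controls at the two sites who come from outside the real waiting list. Let g be the outcome gap, in SD, between them and wait-list controls for reasons unrelated to peer support. Neither is in the documents. I take f = 0.25 to 0.50 and g = 0.2 to 0.4.
- At the two sites, bias = f × g, from 0.25 × 0.2 = 0.05 to 0.50 × 0.4 = 0.20 SD.
- Pooled over three sites, bias = f × g × 143/293, from 0.05 × 0.488 = 0.024 to 0.20 × 0.488 = 0.098 SD.
- Against the pooled detectable effect, 0.0244/0.209 = 12% and 0.0976/0.209 = 47%.

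**5. Effect on the test.** With no true effect, the standardised statistic is shifted by bias × √(n/2), with n per arm.

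| Two-site bias (SD) | Pooled bias (SD) | Type I error, two sites (n = 143) | Type I error, pooled (n = 293) |
|---|---|---|---|
| 0.05 | 0.024 | 0.071 | 0.060 |
| 0.20 | 0.098 | 0.394 | 0.219 |

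The nominal level is 0.05. The pooled column counts only bias from the two non-randomised sites.

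**The case against.** Several points on the other side have force.

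- **Access and eligibility.** The protocol says both groups have access to the agency's other services at Community Place and at Los Angeles, and everyone enrolled must be eligible for a companion. This narrows the gap between the two kinds of control. It does not close it, because access is not use and eligibility is not having asked.
- **Los Angeles.** A reader might infer that Los Angeles also builds a waitlist of non-clients. The text does not support that. Strategy B names no arm and does not use the word. Its meal programs are run by the agency, which lists meals among its services, so attendees are already users. Only Park LaBrea could supply non-clients, and its link to the agency is not described.
- **The warning under Unexpected Circumstances.** It begins "For the control group a problem we may face is the fact that they" and goes on to say that controls may not know the organization. A reader might take this as proof that Community Place controls do not receive the agency's services. It names no site, is framed as a refusal problem, and fits Palm Beach at least as well, where controls are recruited from the community. It makes the mechanism plausible and no more.
- **Unseen data.** The upload list is not the whole dataset. The screening and baseline surveys are separate documents and may record service use, and the SAP allows for unnamed confounders. Even so, the SAP commits to no such adjustment.
- **Avoidability.** A reader might conclude from 408 names for 113 places that the sessions are unnecessary. The protocol calls its counts fluid, and they come before screening, refusal and matching over 3 × 2 × 3 × 2 = 36 cells. The count makes filling from the list plausible but does not establish it.

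**Conclusion.** The conflict over control source is plain at Community Place: the SAP and the Matching section name the waiting list, while strategy C creates a second source that nothing listed distinguishes from the first. At Los Angeles there is a departure from the SAP only if strategy B feeds controls, and possible non-client status is limited to Park LaBrea.

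Size and direction cannot be computed from the documents. Session attendees could be healthier or sicker than wait-list clients, so the bias could create an effect or hide one. Under the assumed ranges it is 0.05-0.20 SD at the two sites and about 0.024-0.098 SD pooled. The pooled figure is the one to set against 0.209 SD, since that effect size belongs to the three-site comparison. Setting the two-site figure against it would roughly double the apparent problem.

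It would go too far to say that the effect at these sites cannot be attributed to peer support at all. The supported conclusion is that the plan, as written, offers no way to check whether it can. It should be corrected, and doing so is cheap.

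**What to change.** 1. Correct the Randomization and matching section of the SAP to name the actual control sources for each site, including which arm Los Angeles strategy B feeds.
2. Record for every control the recruitment source (pre-existing wait list, or session or other) and, for everyone, prior use of the agency's services other than the companion. Do this at enrolment. For anyone already enrolled, complete it from recruitment records where they allow.
3. Add prior agency service use as a named covariate in the regression analyses. Source is defined only for controls, so it is better handled by restriction, as in the next step.
4. Pre-specify a comparison at Community Place and Los Angeles limited to pre-existing wait-list controls and their matched recipients, reported beside the all-control result. State in advance that the effect at these sites is attributed to peer support only if the two agree, and define agreement by estimates and intervals, not by whether both reach significance.

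Reordering recruitment, or resting the conclusion on wait-list controls alone, is not required. That is a debatable trade-off, above all at Los Angeles with 35 listed for 30 places.

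The cost is one or two data fields, some SAP wording and a wider interval in the restricted comparison. If 25-50% of matched pairs drop out of it, the interval widens by 1/√0.75 = 1.15 to 1/√0.50 = 1.41 times, and the loss is likely to fall hardest at Los Angeles.
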